6.2.1. Schedule of Assessments and Procedures

A comprehensive Schedule of Assessments and Procedures is presented in Table 3.

Due to the ongoing COVID-19 pandemic, arrangements may also be made, contingent on the subject's consent and in compliance with country, state, and local requirements, to have a study visit conducted at the subject's home by site staff. If this occurs, blood and/or urine samples may be collected at the subject's home and then sent to the central laboratory for processing and analysis. Study drug may also be delivered to the subject's home, if needed, to enable the subject to continue administering their study drug daily.

Table 3:Schedule of Assessments and Procedures

	Visit	1	2	3	4	5	6	7	8	9
Procedure	Study Day/Month:	Screening	Pretreatmen t	Day 1	Month 1	Month 3	Month 6	Month 9	Month 12/ Early Termination	Month 13 Follow- up
Visit Window (1	Days)	N/A ¹	± 4	± 4	± 4	± 4	± 4	± 4	± 4	± 7
Informed consent		Х								
Verification of e	entry criteria	X	Х							
Physical examin	nation ²	X								
Review of medi	cal history ³	X								
Symptom-directed physical examination			Х	Х	X	Х	Х	Х	Х	Х
Vital signs ⁴		X	Х	Х	Х	X	Х	Х	Х	Х
Weight measurement		X		Х	Х		Х		Х	
Height measurement ⁵		Х	Х	Х	Х	Х	Х	Х	Х	Х
Electrocardiogram ⁶		X		Х					Х	Х
Urinalysis (dipstick) ⁷		X			Х		Х		Х	
Chemistry blood collection		X			Х		Х		Х	
Hematology blood collection		X			Х		Х		Х	
Coagulation (PT and PTT) blood		X							Х	
PTH (1–84)		X							X	
25-hydroxyvitamin D level		X							X	
1,25-dihydroxy vitamin D level		X							Х	
Total testosterone and SHBG		X							Х	
Estradiol		X								
Thyroid stimulating hormone ⁸		X								
PK samples (see Table 4)							Х	X	X	
Study medication assignment via IRT				Х						
Injection training for subjects			Х							

Table 3:Schedule of Assessments and Procedure	s (Continued)
---	---------------

	Visit	1	2	3	4	5	6	7	8	9
Procedure	Study Day/Month:	Screening	Pretreatment	Day 1	Month 1	Month 3	Month 6	Month 9	Month 12/ Early Termination	Month 13 Follow-up
Visit Window (Days	s)	N/A ¹	± 4	± 4	± 4	± 4	± 4	± 4	± 4	± 7
Calcium and vitami	n D supplements		Daily administration							
Study medication ad	dministration		Daily administration							
Serum markers of b (s-PINP and s-CTX	one metabolism			Х	Х	Х	Х		X	
Serum calcium and	albumin ⁹			Х	Х	Х	Х	X		
24-hour urine collection (for calcium:creatinine and creatinine clearance) ¹⁰				Х		Х				
Radiologic (lumbar and thoracic vertebrae) assessments		X								

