Symptom driven spinal radiologic assessment			At any time							
Clinical assessment of new fractures ¹¹			Х	Х	Х	Х	Х	X	X	
BMD of lumbar spine, total hip, and femoral neck by DXA ¹²		X				X	X		X	
BMD of wrist by DXA ¹³				Х		Х	Х		X	
vBMD of hip by QCT ¹⁴				Х					Х	
Sample for immunogenicity testing ¹⁵				Х	Х	Х	Х	Х	X	Х
Investigator assessment of local tolerance (dermal reactions assessment)				Х	Х	Х	Х	Х		
Subject assessment of local tolerance ¹⁶				Х				X		
Subject diary review ¹⁷				Х	Х	Х	Х	Х	X	
Document AEs and concomitant ¹⁸ medications		At any time, question subjects at every visit								
Drug supply/resupply/accountability				Х	X	Х	Х	Х	X	

- 1. The window for screening activities is 60 days. Due to the ongoing COVID-19 pandemic or other local/widespread emergencies, if there is a delay in the screening process that would result in a subject remaining in screening for greater than 60 days, the Medical Monitor should be contacted. All safety laboratory results must be reported within 30 days prior to randomization.
- 2. A complete physical examination includes a review of the following systems: head/neck/thyroid, eyes/ears/nose/throat, respiratory, cardiovascular, lymph nodes, abdomen, skin, musculoskeletal, and neurological. Breast, anorectal, and genital examinations will be performed when medically indicated. After screening, any clinically significant abnormal findings in physical examinations should be reported as AEs.
- 3. Including alcohol and tobacco use assessment.
- 4. Blood pressure, heart rate, body temperature, and respiration rate are to be recorded predose at each study visit. Only blood pressure, heart rate and respiration rate are to be recorded one-hour post dose at each study visit during the Treatment Period. All blood pressure assessments need to be orthostatic.
- 5. Height is to be measured at each visit in the standing position using a medical stadiometer.
- 6. ECGs are to be performed predose and one-hour postdose during the Treatment Period.
- 7. All routine urinalysis will be performed on a sample freshly voided during the visit and sent to a central lab for microscopy if test is positive for micro-organisms via dipstick.
- 8. Reflex testing of T3 and free T4 will be performed by the central laboratory for any out-of-range TSH result.

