6.5. Laboratory Evaluations

6.5.1. Clinical Laboratory Evaluations

Hematology, serum chemistry, and urinalysis will be collected at time points indicated in the Schedule of Assessments and Procedures in Table 3. All clinical laboratory blood and 24-hour urine samples will be sent to a central laboratory for analysis and testing. A list of study clinical laboratory tests is in Table 5.

Hematology	Serum Chemistry	Urinalysis (Dipstick) ^a	Additional Tests
Hemoglobin	Sodium	pH	PTH (1-84) ^b
Hematocrit	Potassium	Glucose	25-hydroxyvitamin D ^b
			1,25-dihydroxy vitamin D ^b
WBC count with	Chloride	Protein	BSAP
differential in absolute			
counts			
RBC count	Inorganic phosphorus	Ketones	Estradiol
MCV	Albumin	Bilirubin	l estosterone ^b
MCHC	Total protein	Blood	SHBG [®]
МСН	Glucose	Urobilinogen	$1SH (13 \text{ and Free } 14)^c$
Platelet count	BUN	Specific gravity	
	Creatinine	Nitrite	
	Uric acid	Leukocytes	
	AST		
	ALT		
	GGT		
	СРК		
	Alkaline phosphatase		
	Total bilirubin		
	LDH		
	Total Cholesterol		
	Triglycerides		
	Total calcium		

Table 5: Clinical Laboratory Tests

a. Clinic only, if required by PI send to central lab for microscopy

b. Only required at Screening and Visit 8 or early termination (Month 12 visit)

c. Only required at Screening. Reflex testing for T3 and Free T4 will be performed by the central laboratory if TSH is outside the normal limits. Reflex testing for bone-specific alkaline phosphatase will be performed by the central laboratory if serum alkaline phosphatase is outside the normal limits.

ALT = alanine aminotransferase; AST = Aspartate aminotransferase; BSAP = bone-specific alkaline phosphatase; BUN = blood urea nitrogen; CPK = Creatine phosphokinase; GGT = gamma-glutamyl transpeptidase; LDH = lactate dehydrogenase; MCH = mean corpuscular hemoglobin; MCHC = mean corpuscular hemoglobin concentration; MCV = Mean corpuscular volume; PTH = parathyroid hormone; RBC = red blood cell; SHBG = sex hormone binding globulin; TSH = thyroid stimulating hormone; WBC = white blood cell

In the event of medically significant, unexplained, or abnormal clinical laboratory test values, the test(s) should be repeated and followed up until the results have returned to within the normal range or an adequate explanation for the abnormality is found. Clinically significant changes in laboratory tests that occur during the course of the study are to be reported as AEs.

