8.5. Sample Size Calculation

A study sample size of 225 subjects (150 in the abaloparatide-SC group and 75 in the placebo group) will provide at least 99% power to detect a mean difference of 6.5% in the percentage change from baseline in lumbar spine BMD at 12 months between the abaloparatide-SC and the placebo groups at a 2-sided alpha level of 0.01, assuming a SD of 6.0% and a drop-out rate of 10%. For the key secondary endpoints, this total sample size of 225 subjects will have 96% power to detect a 2.2% mean difference (SD = 3.5%) of percent change in total hip BMD at 12 months, and 80% power to detect a 2.0% mean difference (SD = 4.1%) of percent change in femoral neck BMD at 12 months.

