## Potentially Clinically Significant Laboratory Values

Criteria for determining values of laboratory tests that are considered Potentially Clinically Significant (PCS) are in Appendix B of this SAP. The number (%) of subjects with at least 1 post-baseline PCS values who did not have PCS values at baseline will be presented for each laboratory parameter. Results from unscheduled visits will be included in identification of subjects with post-baseline PCS values, as applicable. For the calculation of the percentages of subjects, the denominator will be based on the number of subjects who had no PCS values at baseline and had at least one post-baseline assessment for the specific laboratory parameter of interest. The numerator will be based on the number of subjects from the denominator who had at least one PCS value post-baseline for the specific laboratory parameter of subjects with any PCS values will be provided.

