Absolute Eosinophils		>5000 cells/mm 		>5.00 10  /L
Absolute Lymphocytes	≤499 cells/mm 		≤0.499 10  /L	
Absolute Neutrophils	≤999 cells/mm 		≤0.999 10  /L	
Hemoglobin	$\leq 10.4 \text{ g/dL} \text{ (male)}$	change from baseline ≥2.1 g/dL	$\leq 104 \text{ g/L} \text{ (male)}$	change from baseline ≥21 g/L
Platelets	≤99000 cells/mm 		≤99 10  /L	
White Blood Cells	$\leq$ 1499 cells/mm 	$\geq$ 20001 cells/mm 	≤1.499 10  /L	≥20.0 10  /L
Coagulation				
Activated Partial Thromboplastin Time		≥1.41*ULN		≥1.41*ULN
Serum Chemistry				
Alanine Aminotransferase		≥5.1*ULN		≥5.1*ULN
Albumin	<2.5 g/dL		<25 g/L	
Alkaline Phosphatase IFCC		≥3.1*ULN		≥3.1*ULN
Aspartate Aminotransferase		≥5.1*ULN		≥5.1*ULN
Bilirubin Total		≥1.51*ULN (with ALT and/or AST>ULN)		≥1.51*ULN (with ALT and/or AST>ULN)
		$\geq$ 2.0*ULN (with normal liver function tests)		≥2.0*ULN (with normal liver function tests)
Calcium	≤7.4 mg/dL	≥11.6 mg/dL	≤1.85 mmol/L	≥2.9 mmol/L
Cholesterol Total		>226 mg/dL		>5.8534 mmol/L
Creatine Kinase		≥3.1*ULN		≥3.1*ULN
Creatinine		$\geq 2.1 \text{ mg/dL}$		$\geq$ 185.64 umol/L
Glucose	$\leq$ 54 mg/dL	>200 mg/dL (random)	$\leq$ 2.997 mmol/L	> 11.1 mmol/L
Potassium	≤3.2 mEq/L	≥5.5 mEq/L	$\leq$ 3.2 mmol/L	≥5.5 mmol/L
Protein Total	<5 g/dL		<50 g/L	
Sodium	≤129 mEq/L	≥148 mEq/L	$\leq 129 \text{ mmol/L}$	≥148 mmol/L
Urine				
Glucose		2+ (≥100 mg/dL)		2+ (≥5.55 mmol/L)
Protein		2+ (≥100 mg/dL)		$2+ (\geq 1.0 \text{ gm/L})$
Blood (microscopic)		>50 rbc/hpf		>50 rbc/hpf
Source: FDA Guidance for Indus and Adolescent Volunteers Enrol	try 2007, Toxicity Gradi led in Preventive Vaccin	ng Scale for Healthy Adult e Clinical Trials		

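### The urine-blood row in SAP Appendix B rests on microscopy done only when triggered, so its percentage describes men selected after randomisation and not the Safety population

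*SAP*

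**What the plan says.** **Criterion.** The Urine block of SAP Appendix B has three rows. Glucose and protein are each flagged at grade 2+. Blood is flagged only as "Blood (microscopic"), above 50 red cells per high-power field. There is no row for dipstick blood.

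**Routine test.** Protocol Table 3 schedules urinalysis by dipstick at Screening and Months 1, 6 and 12 or early termination. Protocol Table 5 includes blood on the dipstick panel.

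**Microscopy.** Protocol Table 3 footnote 7, repeated as SAP Table 1 footnote 6, has the sample "sent to a central lab for microscopy if test is positive for micro-organisms via dipstick". Footnote a to Protocol Table 5 reads "Clinic only, if required by PI send to central lab for microscopy". Neither footnote names dipstick blood as a trigger.

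**Percentage.** In SAP 4.5.6, under Potentially Clinically Significant Laboratory Values, the denominator is men with no PCS value at baseline who "had at least one post-baseline assessment for the specific laboratory parameter of interest". The rule continues: "The numerator will be based on the number of subjects from the denominator who had at least one PCS value post-baseline". Unscheduled results count when PCS values are identified.

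**Other outputs.** SAP 4.5.6 also plans shift tables for urinalysis by normal-limit category, and listings of all laboratory data with out-of-range results marked.

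**The concern.** The criterion needs a cell count, and a count exists only where microscopy was done. A man whose dipstick shows blood, but who meets neither trigger, has no result for this parameter. He is not counted as free of a PCS value; he is absent from both numerator and denominator.

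All post-baseline microscopy is triggered by something seen or decided after randomisation. The two arms' percentages can therefore differ because different shares of men were sent for microscopy, and not only because urine blood differed. The row will stand in the same table as percentages for tests scheduled in every man, and a reader will naturally take it for a Safety-population rate. What is at stake is the meaning of one descriptive safety row.

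**Working it through.** The documents give no microscopy rate, expected PCS rate or expected denominator, so there is no planned figure to reproduce. The check is a cross-reading, followed by an illustration of scale.

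**Step 1: follow one man through the rules**

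| Post-baseline course | Dipstick blood result? | Microscopy result? | In the PCS row? |
|---|---|---|---|
| Dipstick positive for micro-organisms | Yes | Yes (footnote 7) | Yes |
| No such finding; investigator requests microscopy | Yes | Yes (footnote a) | Yes |
| No such finding; no request, whatever the dipstick blood grade | Yes | No | No |

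The third line follows from the microscopy-only criterion, the conditional test and the parameter-specific denominator taken together. A selected denominator is thus a direct consequence of the text. Its size is not.

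**Step 2: baseline**

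Screening urine is also a dipstick with conditional microscopy. The SAP does not say whether a man without baseline microscopy counts as having no PCS value at baseline. If a baseline result were required, the denominator would shrink further.

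**Step 3: scale, under an assumption**

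The planned size is "225 subjects (150 in the abaloparatide-SC group and 75 in the placebo group") (Protocol 8.5). Let f be the share of men with any post-baseline microscopy. This is an assumption, varied from 5% to 30%. Suppose one man per arm is flagged and is among those examined. Then

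- denominator n = planned arm size × f, rounded to a whole man;
- percentage p = 1/n;
- 95% Wilson interval = [p + z²/(2n) ± z√(p(1−p)/n + z²/(4n²))] / (1 + z²/n), with z = 1.96.

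| f | Abaloparatide-SC | Placebo |
|---|---|---|
| 5% | 1/8 = 12.5% (2.2 to 47.1) | 1/4 = 25.0% (4.6 to 69.9) |
| 10% | 1/15 = 6.7% (1.2 to 29.8) | 1/8 = 12.5% (2.2 to 47.1) |
| 20% | 1/30 = 3.3% (0.6 to 16.7) | 1/15 = 6.7% (1.2 to 29.8) |
| 30% | 1/45 = 2.2% (0.4 to 11.6) | 1/22 = 4.5% (0.8 to 21.8) |
| All examined | 1/150 = 0.7% (0.1 to 3.7) | 1/75 = 1.3% (0.2 to 7.2) |

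Relative to examining everyone, the same single case gives a percentage between 150/45 = 3.3 and 75/4 = 18.8 times larger. The roughly two-fold gap between arms within each line comes from the 2:1 allocation with one case per arm, and is not itself a sign of bias.

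**Step 4: unequal testing**

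If 10% of the active arm and 20% of placebo were examined (again assumed), the denominators would be 150 × 0.10 = 15 and 75 × 0.20 = 15. One case each would print as 6.7% in both arms, where full testing would give 0.7% and 1.3%. The contrast between arms then depends on who was tested.

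**The case against.** The best reply is that little is lost. Dipstick blood is within the urinalysis shift tables and the listings. Protocol 6.5.1 requires abnormal values to be repeated and followed up, and clinically significant changes to be reported as adverse events. SAP 4.5 treats safety outputs as descriptive, and no test is planned for the PCS rows. All of this stands and limits the point to one row. It does not correct that row's denominator.

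Several stronger readings are tempting, but the documents do not support them:

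- **Only a few men will have microscopy.** No rate is given. That the men are selected is certain; how many there are is not.
- **A man with strongly positive dipstick blood can never be flagged.** This holds only if footnote 7 is read alone. Footnote a lets the investigator send any sample, and unscheduled results count.
- **Isolated haematuria goes unreported.** The shift tables, listings and adverse event reporting remain open to it.
- **The two triggers contradict each other.** One can be automatic and the other discretionary, so they can coexist. The plan simply never says how they combine.
- **The row matters because it stands in for hypercalciuria or stones.** The documents make no such link. Hypercalciuria is assessed from scheduled 24-hour urine at Day 1 and Month 3, and haematuria is not among the adverse events of special interest.

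It can also be said that the microscopic form was the sponsor's choice, since Appendix B cites an external toxicity scale, and that dipstick blood is less specific. Both are fair. They are reasons to keep the microscopic row as supporting data, not to leave it as the only urine-blood criterion.

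**Conclusion.** The point holds, narrowly. As written, the PCS percentage for urine blood is a rate among men who had post-baseline microscopy because of a micro-organism-positive dipstick or an investigator's request. It is not a Safety-population rate, and the comparison between arms is conditional on events after randomisation.

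The size of the distortion cannot be fixed from the documents. With an assumed 5% to 30% of men examined, one case per arm prints at about 3 to 19 times its value under full testing. Those multiples rest on the planned arm sizes, on equal testing in both arms, and on the flagged man being among those examined.

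This is a cheap improvement to one descriptive row. The primary and key secondary analyses, the 1% significance level and the power statement are untouched.

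**What to change.** 1. In SAP Appendix B, add a urine-blood criterion on the dipstick grade, in the form already used for urine glucose and protein: 2+, or another grade that the sponsor fixes before unblinding. Its denominator would be close to complete, because the dipstick is scheduled for every man at Screening and at three post-baseline visits.
2. Keep the microscopic criterion as supporting data. Show the number of men with post-baseline microscopy by arm beside the percentage, note that testing was conditional, and state how a man without baseline microscopy is handled.
3. State in one place how the microscopy triggers in Protocol Table 3 footnote 7 (SAP Table 1 footnote 6) and Protocol Table 5 footnote a work together.

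**Cost.** One added row, one table note and one footnote clarification, with no new test. This assumes that the dipstick blood grade is captured in the database, as the 2+ rows for glucose and protein appear to require for those analytes. The downside is lower specificity: some men flagged by dipstick would not meet the microscopic criterion. If the sponsor prefers not to add the row, item 2 alone would at least make the present percentage readable.

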## Appendix B. Criteria for Potentially Clinically Significant Laboratory Values

Parameter	Unit	Lower Criteria	Upper Criteria
Heart Rate	bpm	< 45	>100
			>130
Supine systolic blood pressure	mm Hg	< 80	>155
Supine diastolic blood pressure	mmHg		>100
Standing systolic blood pressure	mmHg	<80	>155
Standing diastolic blood pressure	mmHg		>100
Body temperature	°C		≥39.0

## Appendix C. Criteria for Potentially Clinically Significant Vital Signs Values

#### **Appendix D.** Conventions for Imputing Missing Dates

#### 1. Adverse event (AE) start (onset) date imputation

AE start (onset) date is separated into 3 different data fields, including day, month, and year. Completely missing AE start date (i.e., missing day, missing month, and missing year) will not be imputed. Partial AE start date will be imputed according to treatment start date as follows in a sequential fashion.

- If AE year is missing, then no imputation
- If AE month and day are missing and
  - if AE year < Treatment year then AE month/day = '01JUL'
  - if AE year = Treatment year then AE month/day = treatment start date+1
  - if AE year > Treatment year then AE month/day = '01JAN'
- If AE day is missing and
  - if AE year < Treatment year then AE day = '15'
  - if AE year = Treatment year and
    - > if AE month < Treatment month then AE day = '15'
    - $\blacktriangleright$  if AE month = Treatment month then AE date = treatment start date+1
    - if AE month > Treatment month then AE day = '01'
  - if AE year > Treatment year, then AE day = (01)
- If AE start date is still missing after the above imputation and AE end date is nonmissing then AE start date = AE end date.
- If AE start date is still missing after the above imputation, then count this AE as a treatmentemergent AE.

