7. ADVERSE EVENT AND SERIOUS ADVERSE EVENT DOCUMENTATION

7.1. Evaluation of Safety

Timely, accurate, and complete reporting and analysis of safety information from clinical studies are crucial for the protection of subjects and is mandated by regulatory agencies worldwide. All clinical studies sponsored by RADIUS will be conducted in accordance with Standard Operating Procedures (SOPs) that have been established to conform to regulatory requirements worldwide to ensure appropriate reporting of safety information.

All AEs are collected from the time of the informed consent until 30 days after last dose of investigational product. Where possible, a diagnosis rather than a list of symptoms should be recorded. All AEs should be captured on the appropriate AE pages in the eCRF and in source documents. The Investigator will assess all AEs for relationship to study drug. For information on the safety profile obtained to date for abaloparatide, please refer to the IB.

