#### 4.5.3 Adverse Events

All adverse events (AEs) will be coded by System Organ Class (SOC) and Preferred Term (PT) using the MedDRA (Version 24.0) coding system. Analyses of AEs will be performed for those events that are considered to be Treatment-Emergent Adverse Events (TEAEs). A TEAE is defined as any AE that was absent (i.e., had not occurred) or had resolved prior to the start of

study drug, and which occurred on or after the date of the first dose of study drug and within 30 days of the last dose of study drug; or any AE that started prior to the first dose of study drug, was ongoing after study treatment started, and increased in severity after the start of study drug and within 30 days of the last dose of study drug. AEs with missing onset dates will be handled according to the Conventions for Imputing Missing Dates in Appendix D.

In any tabulation of adverse events, a subject contributes only once to the count for a given SOC or PT. For summaries by severity, a subject with multiple occurrences of an AE will be represented under the most severe occurrence. For summaries by relationship to study drug, a subject with multiple occurrences of an AE will be represented under the most related occurrence.

An overall summary of the adverse events will be provided, in which the number of subjects with any adverse events, number of subjects with any TEAEs, number of subjects with any treatment-related TEAEs, number of subjects with any severe TEAEs, number of subjects with any treatment-related severe TEAEs, number of subjects with any serious TEAEs, number of subjects with any TEAES leading to study drug withdrawal, number of subjects with any TEAEs leading to study drug interruption, number of subjects with any TEAEs leading to study discontinuation, and number of subjects with any TEAEs leading to death will be summarized by treatment groups.

The following summaries will also be presented:

- TEAEs by SOC and PT
- TEAEs by SOC, PT, and region (North America and Europe)
- TEAEs by PT. Note: TEAEs will be sorted in descending order of total number of subjects with the preferred term in the abaloparatide-SC treatment group
- TEAEs by SOC, PT, and maximum severity
- Severe TEAEs by SOC and PT
- Treatment-related severe TEAEs by SOC and PT
- TEAEs by SOC, PT, and relationship to study drug
- Treatment-related TEAEs by SOC and PT
- TEAEs leading to study drug interruption by SOC and PT
- TEAEs leading to study drug withdrawal by SOC and PT

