## 3. Other date imputations

Any event with a partial date that requires imputation but has no specific imputation rule will be imputed as follows:

- If the day is missing, then impute the day as '01'
- If the month is missing, then impute the month as 'JUL'
- If the imputation of a start date causes the start date to be post the non-missing end date, then the start date will be imputed as the end date.
- If the imputation of a start date causes the start date to be prior to the start of treatment (but the event should happen post-baseline), then the start date will be imputed as "treatment start date + 1."

Any date cannot be imputed past the date of death. When this happens, the date will be imputed as the date of death.

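### SAP Appendix D, part 1 sets some partial AE onset dates to the day after first dose without checking the AE end date, so an event known to have ended before dosing can be counted as treatment-emergent

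*SAP*

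**What the plan says.** SAP section 4.5.3 defines a treatment-emergent AE (TEAE) mainly by its onset: an event that was absent or had resolved before study drug started, "which occurred on or after the date of the first dose of study drug" and no later than 30 days after the last dose. For incomplete onsets the section adds: "AEs with missing onset dates will be handled according to the Conventions for Imputing Missing Dates in Appendix D".

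Appendix D, part 1 fills in a partial onset from the known parts of the date and the treatment start date. Two of its branches give the day after first dose:

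- month and day missing: "if AE year = Treatment year then AE month/day = treatment start date+1";
- day missing, same year as first dose: "if AE month = Treatment month then AE date = treatment start date+1".

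The AE end date is used once in part 1, as a later fallback: "If AE start date is still missing after the above imputation and AE end date is nonmissing then AE start date = AE end date".

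Part 3 of the appendix covers other dates. Its scope is "Any event with a partial date that requires imputation but has no specific imputation rule will be imputed as follows". It includes a check that begins "If the imputation of a start date causes the start date to be post the non-missing end date" and resets the start to the end date.

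On data collection, protocol section 7.1 says: "All AEs are collected from the time of the informed consent until 30 days after last dose". Protocol section 8.4.5 requires AEs from before the first dose to be summarized separately, and SAP section 4.5.3 plans a table of non-TEAEs.

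**The concern.** AE recording starts at consent, and up to about 67 days can pass before dosing (60 days of screening plus 1 week of pretreatment). Some AEs will therefore start and end before any study drug is given. If such an event has a partial onset that falls in one of the two branches, the plan moves its onset past its own recorded end and past the first dose. It then leaves the pre-dose summary, where the protocol puts it, and enters the TEAE tables.

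The AE of special interest (AESI) summaries in SAP section 4.5.3 are also exposed, because they report onset time and duration. A wrongly dated record appears as a very early event, and its duration is negative, which fits none of the listed duration groups and pulls down the mean and minimum.

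**Working it through.** The documents state no figure on this point, so there is nothing to reproduce. The check is a literal application of the rules.

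**1. Which branches are affected.** Part 1 has three branches for month and day missing (year before, equal to or after the treatment year). It has five for day missing (earlier year; same year with earlier, same or later month; later year). That makes 3 + 5 = 8, of which two give first dose + 1. The others give 1 July, 1 January, the 15th or the 1st.

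**2. Whether any other text intervenes.** The part 1 fallback to the end date needs an onset that is still missing, which cannot be so after either branch. The part 3 check is confined to dates without a specific rule, and AE onset has one. The TEAE definition does not help either, because the imputed onset satisfies its on-or-after-first-dose condition.

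**3. Worked records.**

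| First dose | Recorded onset | Recorded end | Imputed onset | TEAE? | Onset minus end |
|---|---|---|---|---|---|
| 20 Mar | unknown day, Mar | 10 Mar | 21 Mar | yes | 21 − 10 = 11 days |
| 20 Sep 2019 | unknown day, Sep 2019 | 12 Sep 2019 | 21 Sep 2019 | yes | 21 − 12 = 9 days |
| 20 Sep 2019 | unknown day and month, 2019 | 10 Aug 2019 | 21 Sep 2019 | yes | 21 + 21 = 42 days |
| 20 Sep 2019 | unknown day, Aug 2019 | 10 Aug 2019 | 15 Aug 2019 | no | 15 − 10 = 5 days |

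The last row shows another branch that can place onset after end, but the event stays before first dose and is classified correctly.

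In the first row the duration is 10 − 21 = −11 days as a plain difference, or −10 if 1 is added as the SAP does for exposure. The SAP gives no formula for AE duration. By the study-day formula in SAP section 3.2 the imputed onset is day 2. If AESI onset time is counted that way, the record falls in the 2–3 day group.

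**4. How often an eligible record is affected.** The rules were applied to every first-dose date in one calendar year (2019), crossed with every pre-dose onset day. Assumptions: dates evenly spread, AE duration 0 to 7 days, AE ended before first dose.

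| Pre-dose window | Only day missing | Month and day missing |
|---|---|---|
| 30 days | 38–49% become TEAEs | 95–96% |
| 67 days | 14–22% | 90–91% |

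These are shares of AEs that ended before dosing and already have a partial onset of that kind. They are not shares of all AEs. With the part 3 check applied, every cell is 0%.

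**5. Ceiling on a TEAE rate.** At the planned arm sizes, one man is 1/150 = 0.67 points on abaloparatide and 1/75 = 1.33 points on placebo. SAP section 4.5.3 counts a subject once per system organ class or preferred term, so the shift occurs only if he has no other TEAE in that row.

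**6. Completely missing onset.** Part 1 opens by saying that such a date is not imputed, yet a later step gives a still-missing onset the end date, and the last step counts anything still missing as a TEAE. Two readings follow:

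| Known end date | Opening sentence governs | End-date step governs |
|---|---|---|
| Before first dose | TEAE | not a TEAE |
| First dose to 30 days after last dose | TEAE | TEAE |
| More than 30 days after last dose | TEAE | not a TEAE |

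The readings disagree at both ends.

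**The case against.** Placing an ambiguous onset after first dose is a sound conservative convention: it tends to over-count TEAEs rather than hide them. The rule is the same in both arms, the safety analyses are descriptive, and no efficacy result depends on it. AEs are collected prospectively with questioning at every visit, and protocol section 9.7 has missing or discrepant data queried, so an AE with a known end but no onset month should be rare. All of that stands and keeps the point small. It does not justify the convention where a recorded end date removes the ambiguity.

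A reader might infer more than the documents support:

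- **That all partial onsets go to first dose + 1.** Only two of the eight branches do this. With only the day missing, the AE must fall in the calendar month of first dose.
- **That every affected man shifts the TEAE rate by 0.67 or 1.33 points.** Those are ceilings, and they use planned arm sizes rather than Safety population counts.
- **That on-treatment events with no onset date and a late resolution drop out of the TEAE tables.** This follows on one reading only. The opening sentence of part 1, with its last step, keeps them in. What can be shown is a conflict in the text.
- **That any AE with no onset date can safely be called treatment-emergent because nothing is collected beyond 30 days after the last dose.** Protocol section 7.1.4 also requires related serious AEs to be reported at any time after study completion. Such an event could then become a TEAE against the 30-day limit.

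**Conclusion.** The point holds for the two branches: as written, they can turn an AE known to have ended before first dose into a TEAE that starts after it ended. This contradicts the separate pre-dose summary in protocol section 8.4.5. The conclusion rests on the text alone and needs no assumption about the data. The practical size does depend on the data: the documents give no count of affected records, and it is probably small. The AESI onset and duration summaries are affected only if such a record is an AESI. The lines on a completely missing onset are a separate drafting conflict to be reconciled; the documents do not establish which way those events would be classified. This is a low-severity correction worth making because it is cheap.

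**What to change.** In SAP Appendix D, part 1:

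1. After the partial-date rules, add the part 3 check: if the imputed AE onset is later than a non-missing AE end date, set onset to the end date. State that an AE which ended before first dose is not treatment-emergent. The first worked record then has onset 10 March and is not a TEAE. An AE that ended on the day of first dose gets that day as onset and remains a TEAE, so the conservative convention survives where the timing is truly unclear.
2. Reconcile the lines on a completely missing onset. Count the AE as treatment-emergent when its end date is on or after first dose, except when it is known to have begun more than 30 days after the last dose, such as a related serious AE reported after the study.

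The cost is a few sentences and a small change to the AE dataset program before database lock. No data collection or efficacy analysis changes.
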